3.1 Study Design

This is a Phase 3, open-label, international, randomized study to evaluate the efficacy and safety of ¹⁷⁷LuPSMA-617 in patients with progressive PSMA positive mCRPC, when administered in addition to best supportive/best standard of care (BSC/BSoC) as compared to BSC/BSoC alone (Figure 1).

Figure 1 Diagram of trial design

ECOG = Eastern Cooperative Oncology group; EQ-5D-5L = European Quality of Life (EuroQoL) – 5 Domain 5 Level scale; FACT-P = Functional Assessment of Cancer Therapy – Prostate; mCRPC = metastatic castration-resistant prostate cancer; PSMA+ = prostate-specific membrane antigen positive; RECIST = Response Evaluation Criteria in Solid Tumors

BSC/BSoC includes available care for the eligible patient according to best institutional practice and at the discretion of the investigator. Novel androgen axis drugs [NAADs] (i.e., enzalutamide, abiraterone, or apalutamide) are allowed.

Investigational agents, cytotoxic chemotherapy, immunotherapy, other systemic radio isotopes (e.g. radium-223) or hemi-body radiotherapy treatment may not be administered on study.

At screening, potential subjects will be assessed for eligibility and will undergo a ⁶⁸Ga-PSMA-11 PET/computed tomography (CT) scan to evaluate PSMA positivity. Only patients with PSMA-positive cancer will be randomized in a 2:1 ratio to receive either ¹⁷⁷Lu-PSMA-617 plus BSC/BSoC (investigational arm) or to receive BSC/BSoC only (BSC/BSoC-only arm). Randomization will be stratified by 4 factors (Section 3.2).

Patients randomized to the investigational arm must begin ¹⁷⁷Lu-PSMA-617 dosing within 28 days of randomization. These patients will receive BSC/BSoC and 7.4 GBq ($\pm 10\%$) ¹⁷⁷Lu-PSMA-617 once every 6 weeks (± 1 week) for a maximum of 6 cycles.

After the Cycle 4 dose of ¹⁷⁷Lu-PSMA-617 and prior to Cycle 5 Day 1, the investigator should determine if:

- The patient shows evidence of response (i.e. radiological, Prostate-specific antigen (PSA), clinical benefit) and
- Has signs of residual disease on CT with contrast/MRI or bone scan and
- Has shown good tolerance to the ¹⁷⁷Lu-PSMA-617 treatment.

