 - Rule 2 (Progression at week 16 or later confirmed at next scan): For scans after the first post-treatment scan, there must be at least two new lesions relative to the first post-treatment scan (treating as a new baseline) that remain persistent (confirmed) on a subsequent scan. The date of progression is the date of the scan that first documents the second lesion compared to first post-treatment scan.
- Date of Censoring for rPFS:
 - The censoring date is the date when the last evaluable radiographic assessment (CT/MRI/bone scan) determined a lack of progression.
 - If there were no evaluable assessments, censoring occurs at the date of randomization.
 - Patients who have 2 or more consecutive missed tumor assessments immediately prior to progressive disease (PD) or death will be censored at the date of the last evaluable tumor assessment prior to those missing tumor assessments. Study scans are every 8 weeks +/- 4 days for the first 24 weeks, then every 12 weeks +/- 4 days and are scheduled relative to date of first dose of randomized treatment. Thus, subjects are considered as having 2 missed assessments if:
 - $\text{day } 117 \leq \text{study day of event scan} \leq \text{day } 229$ and time since last evaluable assessment ≥ 118 days
(2 missed visits, $117 = 16 \text{ weeks} + 4 \text{ days} + 1$; $229 = 24 \text{ weeks} + 8 \text{ weeks} + 4 \text{ days} + 1$)
 - $\text{day } 230 \leq \text{study day of event scan} \leq \text{day } 313$ and time since last evaluable assessment ≥ 146 days

(2 missed visits, 145 = 20 weeks + 4 days + 1; 313 = 24 weeks + 20 weeks + 4 days +1)

- study day of event scan \geq day 314 and time since last evaluable assessment \geq 174 days

(2 missed visits, 173 = 24 weeks + 4 days + 1)

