- Analysis as per the primary rPFS analysis but censoring COVID-19 related deaths at the last adequate assessment prior to the death.
- An analysis as per the 'first sensitivity analysis' but censoring COVID-19 related deaths at the date of death.

For the analyses above, the patients with COVID-19 related deaths will be determined in a blinded fashion by clinical review of the data and will be documented prior to database lock.

The same analyses conventions used for the primary analyses of rPFS, as described in section 8.2.1, will be performed (without p-values).

Supportive analyses of rPFS:

rPFS will be derived in all patients randomized (FAS population) using the same conventions as described in Section 8.1.1 but will consider patients randomized before March 5, 2019 who withdrew consent from the study (i.e. no further data on radiographic progression is available) as (1) censored at time of withdrawal and (2) a rPFS event at the time of withdrawal.

The following data will be summarized using the FAS:

- (1): Number (%) rPFS events (radiographic PD, deaths) and censored, reason censored (ongoing without event, withdrew consent, event documented with two or more missed tumor assessments, adequate assessment not available)
- (2): Number (%) rPFS events (radiographic PD, deaths, withdrew consent) and censored, reason censored (ongoing without event, withdrew consent, event documented with two or more missed tumor assessments, adequate assessment not available)

Missing tumor assessments: The number of patients with at least one missing/not evaluable tumor assessment (TA) based on independent central review will be presented together with the following breakdown categories: number of patients with 1, 2, 3, 4, 5, >5 missing/not evaluable TAs. The purpose of this analysis is to gain an insight as to whether the TAs have been carried out in accordance with the protocol and to understand if any meaningful discrepancies exist between the pattern of missing assessments by treatment arms. Timing of all tumor assessments will be depicted graphically and displayed by treatment arm.

Since the planned tumor assessments are every 8 weeks in the first 24 weeks from C1D1 and every 12 weeks thereafter, the following time windows (in weeks) will be constructed for each patient from the date of randomization: (note the open parenthesis such as (12, 20] indicates that week 12 doesn't belong to this interval and week 12+1 day belongs to that interval)

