- Until ~24 weeks post randomization [0, 12], (12, 20], (20, 28]
- After ~24 weeks post randomization (28, 42], (42, 54], (54, 66], ...

where '0' is the patient's date of randomization. Every time-window (with the exception of the initial, broader one) is centered at the scheduled time of a TA, i.e., around week 16, week 24 for second and third window respectively, etc. A patient will be considered 'at risk' of missing a TA for any one of these time-windows if the patient either:

- is 'on study' for at least the first 4 weeks of the time-window for the first 24 weeks (8 weeks for the first time window), or at least the first 6 weeks of time-window thereafter, i.e., if the patient is ongoing at the time of the scheduled TA, or
- discontinued treatment due to documented disease progression within the specific time window.

For example, if a patient discontinued due to documented disease progression during Week 24, then the patient would have been 'at risk' of a missing/not evaluable TA for the [20, 28] week time window.

For the purpose of this analysis, 'not evaluable' TAs (i.e., evaluations with an overall tumor response of 'not evaluable' per central independent review) will be considered to be missing. However, a clear distinction between 'truly missing' and 'present but not evaluable' needs to be made in the derived dataset to allow for both a combined analysis, i.e. missing and not evaluable treated the same, and separate analyses.

TAs performed after a documented radiographic disease progression per independent central review will not be considered. In other words, the final time-window for which a patient would be at risk of a missing/not evaluable scan would be that during which the documented radiographic progression occurred.

For patients without documented radiographic progression per independent central review, all TAs are considered up to the earliest of the following dates: death, the analysis cut-off, discontinuation due to disease progression, withdrawal of consent or loss to follow-up.

Concordance between local and central review: A summary on censoring reasons will be produced for rPFS by investigator and central radiology. The censoring patterns will be compared between investigator and central review. A comparison of rPFS event type/censor between local radiology review and central radiology review will be provided using the PFS-FAS population.

Sensitivity and supplementary analyses for OS:

Supplementary analysis of OS:

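### In the SAP's missing-scan table, the at-risk rule for the (28, 42] window is met at week 34, two weeks before the week-36 scan is due

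*SAP*

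**What the plan says.** The schedule is given in SAP 8.2.1: "Since the planned tumor assessments are every 8 weeks in the first 24 weeks from C1D1 and every 12 weeks thereafter". SAP 8.1.1 adds the tolerance: "Study scans are every 8 weeks +/- 4 days for the first 24 weeks, then every 12 weeks +/- 4 days". Scans are therefore due at weeks 8, 16, 24, 36, 48, 60 and so on; the bone scan forms in Protocol Appendix 11 carry the same later weeks.

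For the missing-assessment table the SAP defines the windows "Until ~24 weeks post randomization [0, 12], (12, 20], (20, 28"] and "After ~24 weeks post randomization (28, 42], (42, 54], (54, 66"], "where '0' is the patient's date of randomization". It then says: "Every time-window (with the exception of the initial, broader one) is centered at the scheduled time of a TA".

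A patient is at risk of missing a scan if on study for the first 4 weeks of a window up to week 24 (8 weeks for the first window). After that the requirement is "at least the first 6 weeks of time-window thereafter, i.e., if the patient is ongoing at the time of the scheduled TA". A second route to being at risk is discontinuation for documented progression within the window. For patients without centrally documented progression, assessments are considered only up to the earliest of death, cut-off, discontinuation for progression, withdrawal of consent or loss to follow-up.

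The stated purpose of the table is to see whether scans were done per protocol and whether missingness differs by arm. The planned output is the number of patients with at least one missing or non-evaluable assessment, broken down as 1, 2, 3, 4, 5 or more than 5.

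**The concern.** The SAP gives a number (6 weeks into the window) and a meaning (ongoing at the scheduled scan) and treats them as the same thing. For (28, 42] they differ. This window is 14 weeks long and the later ones are 12, because it bridges the change from 8-weekly to 12-weekly scanning, yet it keeps the 6-week rule of the 12-week windows. A patient who leaves at week 35 has met the number but not the meaning. If the number governs, he can enter the table as missing a scan that was never due. That would add spurious missing scans just where the schedule changes, in a table meant to show adherence by arm.

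**Working it through.** **Step 1. Each window against its scan.** Inputs: windows and at-risk weeks from SAP 8.2.1; due weeks from the schedule; C1D1 taken as the randomization date. Centre = (lower + upper)/2. At-risk week = lower bound + required weeks on study.

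| Window | Scan due (week) | Centre | At risk from | Due minus at-risk (weeks) |
|---|---|---|---|---|
| [0, 12] | 8 | 6 (stated exception) | 0 + 8 = 8 | 0 |
| (12, 20] | 16 | 16 | 12 + 4 = 16 | 0 |
| (20, 28] | 24 | 24 | 20 + 4 = 24 | 0 |
| (28, 42] | 36 | **35** | 28 + 6 = **34** | **2** |
| (42, 54] | 48 | 48 | 42 + 6 = 48 | 0 |
| (54, 66] | 60 | 60 | 54 + 6 = 60 | 0 |

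The SAP's description is reproduced exactly for every window except (28, 42].

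**Step 2. Does the scan tolerance explain it?** The earliest permitted week-36 scan is 36 − 4/7 = 35.43 weeks. Week 34 is still 1.43 weeks (10 days) earlier, so no.

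**Step 3. Size at the rPFS/interim OS cut-off.** Inputs: 557 patients, 2:1 (about 371 and 186); design median rPFS of 6 and 4 months, i.e. 26.1 and 17.4 weeks; exponential times. Assumption not in the documents: follow-up at cut-off is uniform over 26–61 weeks and independent of rPFS. Affected patients are those event-free whose cut-off falls in weeks 34–36, with no scan yet in the window.

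- Share of cut-offs in weeks 34–36: 2/35 = 5.7%.
- Event-free at week 35: active 2^(−35/26.1) = 0.395; control 2^(−35/17.4) = 0.248.
- Active: 371 × 0.057 × 0.395 ≈ 8.4, or 2.3% of the arm. Control: 186 × 0.057 × 0.248 ≈ 2.6, or 1.4%. Total about 11.
- If every patient cut off after week 35.43 has already been scanned, the exposed span is 1.43 weeks (1.43/35 = 4.1%) and the total falls to about 8.

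Other follow-up patterns scale directly. Each percentage point of cut-offs falling in weeks 34–36 adds 371 × 0.01 × 0.395 + 186 × 0.01 × 0.248 ≈ 1.9 patients.

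**Step 4. Size if rPFS is analysed with final OS.** SAP 4 and 8.2.2 provide for this path. Minimum follow-up is then about 13 months: 13 × 30.4375/7 = 56.5 weeks. No cut-off falls in weeks 34–36, so cut-off exits contribute about zero. Deaths remain. At design OS medians of 10 and 13.7 months, two weeks carry a death risk of 3.1% (control) and 2.3% (active). Applied to patients event-free at week 34 (active 371 × 0.405 ≈ 150; control 186 × 0.258 ≈ 48), this gives about 3.5 + 1.5 = 5 deaths, before removing anyone already scanned in the window. Withdrawals and losses to follow-up would add to this; the documents give no rate for them.

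**The case against.** The strongest reply is that the false counts need not occur. The rule carries its own gloss, and a patient cut off at week 35 is not ongoing at a week-36 scan. The sentence that stops counting assessments at death, cut-off, withdrawal or loss to follow-up can be read to the same effect. This stands in part: a reader might infer that undue scans will be reported as missing, but the text supports only that they could be, because it does not say whether the number, the gloss or the stopping sentence governs.

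A reader might also infer differential missingness between arms. Per arm the shares differ (2.3% against 1.4%), but only because more active patients remain event-free. Among patients still at risk at week 34 with cut-off not yet reached (about 116 and 37, from 27/35 of the event-free numbers), the rates are 8.4/116 = 7.2% and 2.6/37 = 7.1%. Nor is a per-window percentage a planned output, and that denominator leaves out the progression route to being at risk.

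The match of the other windows holds only if C1D1 is the randomization date. Windows start at randomization while scans run from C1D1, and the investigational arm must begin "dosing within 28 days of randomization". With first dose on day 28 the rule runs early by 6 weeks for (28, 42] and by 4 weeks for all the others. That offset is a separate matter; the extra 2 weeks in this window exist even when the two dates coincide.

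Finally, primary rPFS censoring uses its own day limits in SAP 8.1.1, the first sensitivity analysis counts events regardless of missed assessments, and scan timing is also plotted by arm. The documents therefore do not support any effect on the primary result.

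**Conclusion.** The inconsistency is real and exact: (28, 42] is centred on week 35 and its at-risk point is week 34, against a scan due at week 36. Both the centring statement and the equation of 6 weeks with the scheduled scan fail for this window alone, taking C1D1 as randomization. Whether it produces false missing scans depends on which part of the rule is programmed. If it is the number, the effect is about 8–11 of 557 patients at an rPFS/interim OS cut-off, under the assumed uniform follow-up and design medians. On the final OS path it is limited to deaths (about 5 at design hazards), withdrawals and losses. It is confined to one descriptive table: a minor correction worth making.

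**What to change.** In SAP 8.2.1, set the at-risk requirement for (28, 42] to the first 8 weeks of the window, so that 28 + 8 = 36. The first window already has such an exception. In the centring sentence, name (28, 42] as a second exception. Changing the window to (30, 42] would also give week 36, but the preceding window would become (20, 30] with centre 25, so the 8-week rule is cleaner. The cost is one phrase in the SAP and one line of code. The change does not remove the offset between randomization and C1D1, which needs its own decision on the window origin.

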8.2.2 Key Secondary Efficacy Analyses

Refer to Section 8.2 for analysis sets and presentation of summary statistics. To control the overall Type I error rate, if either alternate primary endpoint is met (see Section 4), then the key secondary endpoints will be assessed using the Hochberg closed test procedure at the alpha level applicable to the successful alternate primary endpoint. This procedure is reasonable given the positive correlation between the key secondary endpoints.

The alpha level applicable to the analysis of the key secondary endpoints will depend on the statistically significant results of the final rPFS or the statistically significant results of OS at either the interim or final analysis as follows:

Analysis of Key Secondary Endpoints at Interim and Final OS Analysis

Scenario	Final rPFS/Interim OS Analysis			Final OS Analysis	
	Final rPFS 1-sided p-value	Interim OS 1-sided p-value	2-sided alpha (CI) for Key Secondary Endpoints	Final OS 1-sided p-value	2-sided alpha (CI) for Key Secondary Endpoints
A	p<0.004	p<0.001	0.01 (99%)	Not re-tested ¹	Not re-tested ²
B	p<0.004	NS	Not tested ³	p<0.024	0.048 (95.2%)
				NS	Not tested ⁴
C	NS	p<0.001	0.002 (99.8%)	Not re-tested ¹	Not re-tested ²
D	NS	NS	Not tested ³	p<0.02	0.040 (96%)

NS: Not statistically significant at pre-specified alpha level.

CI: Confidence interval

- Final OS will not be re-tested if the interim OS is met. The final OS results will be presented descriptively including 95% CI and the nominal p-value.
- The key secondary endpoints will not be re-tested if the final OS is met however, the results will be presented descriptively including 95% CI and the nominal p-value.
- The key secondary endpoints will not be tested if interim OS is not met however, the results will be presented descriptively including 95% CI and the nominal p-value.
- If the key secondary endpoints are tested when final OS is not met using the successful rPFS 1-sided (2-sided) alpha level of 0.004 (0.008), there will be, at most, a type I error inflation of 0.004 because the rPFS alpha level has already been allocated to the final OS test. Therefore, if final OS is not met, the key secondary endpoints will only be presented descriptively including 95% CI and the nominal p-value.

Analysis of Key Secondary Endpoints at Final rPFS/Final OS Analysis

Final rPFS/Final OS Analysis			
Scenario	Final rPFS 1-sided p-value	Final OS 1-sided p-value	2-sided alpha (CI) for Key Secondary Endpoints
A	p<0.004	p<0.025	0.05 (95%)
B	p<0.004	NS	Not tested ¹
C	NS	p<0.021	0.042 (95.8%)
D	NS	NS	Not tested ²

NS: Not statistically significant at pre-specified alpha level.

CI: Confidence interval

1. If the key secondary endpoints are tested when final OS is not met using the successful rPFS 1-sided (2-sided) alpha level of 0.004 (0.008), there will be, at most, a type I error inflation of 0.004 because the rPFS alpha level has already been allocated to the final OS test. Therefore, if final OS is not met, the key secondary endpoints will only be presented descriptively including 95% CI and the nominal p-value.
2. The key secondary endpoints will not be tested if final OS is not met however, the results will be presented descriptively including 95% CI and the nominal p-value.

A table summarizing the results of the Hochberg closed test procedure will be provided indicating the applicable alpha level used.

Key secondary endpoints subject to Type I error control:

1. RECIST response: ORR and DCR
2. Time to SSE

Time to Symptomatic Skeletal Event

Time to SSE (defined in Section 8.1.2) will be summarized and analyzed in the same manner as described for rPFS (both primary and supportive analyses using the alpha levels and confidence intervals as described in the table above) using the PFS-FAS, except using 2-sided p-values from the stratified log-rank test as the primary comparison. An additional analysis will be done on the FAS population using the same methods as for the primary analysis.

Overall Response and Disease Control Rate

Percent change of sum of diameters of target lesions (in mm) from baseline per independent central review will be summarized as follows:

- Continuous variable summaries of baseline and best % change from baseline

Overall response rate and disease control rate per independent central review (defined in Section 8.1.2) will be analyzed using logistic regression with a single covariate for randomized treatment arm and stratification for the randomization stratification factors. The following will be reported:

- Odds ratio (active: control) with CI as described in the table above
- The associated 2-sided p-value
- DOR will be displayed using Kaplan-Meier curves, median, 25th percentile, and 75th percentile with 95% CIs, number (%) events and censored, and will be analyzed using mixture distribution methodology (Ellis et al. 2008) outlined below.

The primary analysis of RECIST ORR and DCR will be on the Response Evaluable Analysis Set.

Mixture distribution analysis for duration of response

Duration of Response (DOR) per independent central review will be analyzed in the Response Evaluable Analysis Set using mixture distribution methodology (Ellis et al. 2008). To avoid an inflated estimate of duration of response that occurs when estimating only in the subset of patients that have a response, the following methods, paraphrasing from Ellis et al., will be used. Treatment arm differences in duration of response will be analyzed using a mixture distribution to test the hypothesis that the expected duration of response (EDoR) is equal for the experimental treatment, E, and the control treatment, C, that is:

$$H_0: R = EDoR_E / EDoR_C = 1 \text{ versus } H_a: R = EDoR_E / EDoR_C \neq 1 \quad (1)$$

The test will be performed as follows.

(i) Estimate the proportions of patients with RECIST response as

$$p_E = r_E / N_E \text{ and } p_C = r_C / N_C \quad (2)$$

Where r_E and r_C are the number of patients responding to treatment arms E and C;

N_E and N_C are the number of all patients in each treatment arm.

(ii) Estimate the mean duration of response in each treatment arm, M_E and M_C , and their standard errors, using a time to event probability distribution, in responding patients, some of which may be censored in response. This can be done using SAS PROC LIFEREG for distributions such as the exponential, the Weibull, the gamma, the Normal, and the log Normal. The choice in the distribution will be made based upon overall data (ignoring randomized treatment arm) prior to the planned analysis after the database is locked.

(iii) Combine the estimates from step (i) and (ii) to calculate estimates of R and $Var[\ln(R)]$. Then assess the difference between treatment arms E and C using the test statistic:

$$z = \frac{\ln(\hat{R})}{\sqrt{Var[\ln(\hat{R})]}}$$

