8.3 Sample size and power determination

The sample size was determined based on the alternate primary endpoints of rPFS and overall survival. Planned enrollment for this study is approximately 814 subjects.

Under the null hypothesis for survival, median survival is assumed to be 10 months on ¹⁷⁷Lu PSMA-617 and best supportive/best standard of care (active) for a hazard ratio (HR) of 1.00. Under the alternative hypothesis, median overall survival on active is assumed to be 13.7 months for a HR of 0.7306.

Under the null hypothesis for rPFS, median rPFS is assumed to be 4 months on ¹⁷⁷Lu-PSMA-617 and best supportive/best standard of care (active) for a hazard ratio (HR) of 1.00. Under the alternative hypothesis, median rPFS on active is assumed to be 6 months for a HR of 0.67.

Based on a non-linear patient accrual profile over 14 months, a total of 814 patients randomized and followed on an ITT basis for a minimum of 13 months is expected to yield 508 deaths. This number of events provides at least 90% power to test the hypothesis that the HR for OS is 0.7306 or better with a 1-sided alpha level of at least 0.020.

For rPFS, a total of approximately 557/814 patients are expected to be randomized on or after 5 March 2019, these being the patients to be included in the primary analysis of rPFS; with a minimum of approximately 6 months follow-up, these patients are expected to yield 364 rPFS events which will be sufficient to provide 84% power to test the hypothesis that the HR of rPFS is 0.67 or better with a 1-sided alpha level of 0.004. At the time of this rPFS analysis, 341 deaths are expected amongst all randomized patients. These interim OS data will be analyzed with a 1-sided alpha level of 0.001. Central independent assessments will be used to determine rPFS events.

The alpha level applicable to OS in the final analysis will depend upon the earlier rPFS and interim OS results:

- if $p < 0.004$ 1-sided is achieved for rPFS and $p < 0.001$ 1-sided is achieved for interim OS, then the alpha level for the final analysis of OS will be raised to 0.025 1-sided.
- if $p < 0.004$ 1-sided is achieved for rPFS but $p < 0.001$ 1-sided is not achieved for interim OS, then the alpha level for the final analysis of OS will be 0.024 1-sided.
- if $p < 0.004$ 1-sided is not achieved for rPFS but $p < 0.001$ 1-sided is achieved for interim OS, then the alpha level for the final analysis of OS will be raised to 0.021 1-sided.

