8.9.2 Formal Interim Analysis of OS

As described above in Section 8.3, one formal interim analysis is planned for OS in the FAS to take place at the time of the primary rPFS analysis in the PFS-FAS. The allocated alpha level for the interim OS analysis is 0.001 1-sided. Regardless of whether a positive result is attained at this time, for either rPFS or interim OS, patient follow-up will continue until 508 OS events have accrued in the FAS at which time a final OS analysis will be performed.

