3.4 Sample Size Justification

The sample size was determined based on the alternate primary endpoints of rPFS and overall survival. Planned enrollment for this study is approximately 814 subjects.

Under the null hypothesis for survival, median overall survival is assumed to be 10 months on ¹⁷⁷Lu-PSMA-617 and best supportive/best standard of care (active) for a hazard ratio (HR) of 1.00. Under the alternative hypothesis, median overall survival on active is assumed to be 13.7 months for a HR of 0.7306.

Under the null hypothesis for rPFS, median rPFS is assumed to be 4 months on ¹⁷⁷Lu-PSMA-617 and best supportive/best standard of care (active) for a HR of 1.00. Under the alternative hypothesis, median rPFS on active is assumed to be 6 months for a HR of 0.67.

Based on a non-linear patient accrual profile over 14 months, a total of 814 patients randomized and followed on an ITT basis for a minimum of 13 months is expected to yield

508 deaths. This number of events provides at least 90% power to test the hypothesis that the HR for OS is 0.7306 or better with a 1-sided alpha level of at least 0.020.

For rPFS, a total of approximately 557/814 patients are expected to be randomized on or after 5 March 2019, these being the patients to be included in the primary analysis of rPFS; with a minimum of approximately 6 months follow-up, these patients are expected to yield 364 rPFS events which will be sufficient to provide 84% power to test the hypothesis that the HR of rPFS is 0.67 or better with a 1-sided alpha level of 0.004. At the time of this rPFS analysis, 341 deaths are expected amongst all randomized patients. These interim OS data will be analyzed with a 1-sided alpha level of 0.001. Central independent assessments will be used to determine rPFS events.

The alpha level applicable to OS in the final analysis will depend upon the earlier rPFS and interim OS results:

- if $p < 0.004$ 1-sided is achieved for rPFS and $p < 0.001$ 1-sided is achieved for interim OS, then the alpha level for the final analysis of OS will be raised to 0.025 1-sided.
- if $p < 0.004$ 1-sided is achieved for rPFS but $p < 0.001$ 1-sided is not achieved for interim OS, then the alpha level for the final analysis of OS will be 0.024 1-sided.
- if $p < 0.004$ 1-sided is not achieved for rPFS but $p < 0.001$ 1-sided is achieved for interim OS, then the alpha level for the final analysis of OS will be raised to 0.021 1-sided.

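### If OS is met at the interim, the key secondary endpoints get one test at 2-sided 0.01 or 0.002 and no later test, while the 1-sided 0.020 held for final OS goes unused

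*SAP*

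**What the plan says.** Under SAP 8.2.2, the key secondary endpoints are "assessed using the Hochberg closed test procedure at the alpha level applicable to the successful alternate primary endpoint". The first table there turns this into four scenarios when a formal interim OS analysis is run:

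| Scenario | rPFS | OS met at | Key secondaries tested at | 2-sided alpha |
|---|---|---|---|---|
| A | met | interim | interim | 0.01 |
| B | met | final only | final | 0.048 |
| C | not met | interim | interim | 0.002 |
| D | not met | final only | final | 0.040 |

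In A and C the final-analysis cells allow no further test. For OS: "Final OS will not be re-tested if the interim OS is met". For the key secondaries: "The key secondary endpoints will not be re-tested if the final OS is met however, the results will be presented descriptively", with a confidence interval and a nominal p-value. In B and D the first test waits: "The key secondary endpoints will not be tested if interim OS is not met however, the results will be presented descriptively".

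Protocol 8.3 would have kept a formal final OS test at 1-sided 0.025 or 0.021 after interim success. SAP 2.1 declares that this test is dropped. It does not mention that the key secondaries lose a final test as well, and no other section gives them one.

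**The concern.** With the rPFS result held fixed, meeting OS earlier leaves the key secondaries with less alpha, on data that cannot be more mature. A against B is 0.01 against 0.048; C against D is 0.002 against 0.040. The SAP's own second table shows the same contrast: with no formal interim OS analysis, success on both primaries gives the secondaries 0.05.

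The 1-sided 0.020 held for final OS has no remaining use once OS has been rejected. It could pass to the secondaries but does not. At stake is whether ORR, DCR and time to SSE can support confirmatory claims after an early survival result.

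**Working it through.** **Inputs.** The alphas are from SAP 8.2.2. On timing, SAP 3.4 says "At the time of this rPFS analysis, 341 deaths are expected amongst all randomized patients" and "These interim OS data will be analyzed with a 1-sided alpha level of 0.001". The final OS analysis is at 508 deaths; allocation is 2:1; the design OS hazard ratio is 0.7306.

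**The plan's own figures.** The table's alphas reproduce:
- A: 2 × (0.004 + 0.001) = 0.01
- C: 2 × 0.001 = 0.002
- B: 2 × 0.024 = 0.048
- D: 2 × 0.020 = 0.040

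With information equal to deaths × 2/9, the interim critical hazard ratio is exp(−3.090/√(341 × 2/9)) = 0.701, as stated. Final OS power is Φ(0.3139 × √(508 × 2/9) − 2.054) = 0.900, also as stated.

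**Size of the alpha reduction.** A against B: 0.048/0.01 = 4.8-fold, critical z 2.576 against 1.977. C against D: 0.040/0.002 = 20-fold, critical z 3.090 against 2.054.

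**Illustrative power.** The documents give no effect sizes, event counts or information fractions for ORR, DCR or SSE. I therefore assume one endpoint with 90% power at 1-sided 0.020, so its drift is 2.054 + 1.282 = 3.335. The data are taken as equally mature at both analyses, and power is not conditioned on the OS result.
- A: Φ(3.335 − 2.576) = 0.78
- C: Φ(3.335 − 3.090) = 0.60
- B: Φ(3.335 − 1.977) = 0.91
- D: 0.90 by construction

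With a final re-test at 1-sided 0.020, A and C both return to about 0.90. If the interim data were less mature, the single-look figures would fall. At an assumed information fraction of 0.80 they are 0.66 (A) and 0.46 (C); with the re-test they stay at about 0.90.

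**How likely the branch is.** At hazard ratio 0.7306, the chance of crossing 0.001 at 341 deaths is Φ(0.3139 × √(341 × 2/9) − 3.090) = Φ(−0.358) = 0.36. Scenario C also needs rPFS to fail despite its stated 84% power. If the two were independent, that is 0.36 × 0.16 = 0.06, and less under positive correlation.

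**Error rate of the re-test.** The alpha sums are 0.005 + 0.020 = 0.025 (A) and 0.001 + 0.020 = 0.021 (C), both within the 1-sided 0.025. If the two looks are correlated at √(341/508) = 0.82 (an assumption for these endpoints), the chance of rejecting a null secondary at either look is 0.0215 and 0.0201.

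The branch that applies depends on the data, so A and B were also simulated together, with a null secondary and the design OS effect. Under the re-test rule the error was 0.020 to 0.023, for OS–secondary correlations of 0 to 0.8 and information fractions of 0.67 to 0.99.

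**The case against.** **This is a design preference.** The rule is explicit, pre-specified and conservative, and it follows the principle of testing at the level of the successful primary. A reader might infer a type I error problem; the documents do not support one. But conservatism does not explain why 0.020 is left idle, and the footnote gives no reason.

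**The power loss is easy to overstate.** A reader might apply the OS death fraction, 341/508 = 67%, to the secondaries and get 56% (A) and 36% (C). That fraction describes deaths among all randomized patients. ORR and DCR are response proportions in evaluable patients randomized on or after 5 March 2019, with about 6 months' minimum follow-up by then. SSE data stop at the end-of-treatment visit. Equally mature data is the fairer starting point.

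**Scenarios A and C arise only after OS has crossed 0.001.** Time to SSE counts death as an event, so it should correlate with OS. Given interim success at the design effect, the illustrative power becomes 87% (A) and 72% (C) at correlation 0.3, and 92% and 80% at correlation 0.5. The re-test level of 0.020 gains too (95% and 98%), so a gap remains. Nor is the loss necessarily large when treatment works best: an endpoint with 99% power at 0.020 keeps 96% (A) and 90% (C) with equally mature data.

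**The final look may not happen.** Protocol 8.9.2 says "patient follow-up will continue until 508 OS events have accrued in the FAS" whatever the interim result. But Protocol 8.9.1 and SAP 4.1 let the IDMC recommend early stopping for efficacy, with the sponsor deciding. This point stands, and the fix is conditional for that reason.

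**Validity across branches.** The worst-case sum over A and B is 0.005 + 0.024 = 0.029, and the union at correlation 0.82 is 0.0253. The current table has the same bound, since it already tests at 0.005 in A and 0.024 in B. The re-test at 0.020 does not raise it.

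**Conclusion.** The point holds as a loss of power. The direction follows from the SAP alone: after interim OS success the alpha is 4.8-fold (A) or 20-fold (C) smaller than after success only at the final analysis, with data no more mature and no second test.

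The size is illustrative: roughly 90% falling to 78% (A) or 60% (C). It rests on one endpoint, equal maturity and no conditioning on OS. Less mature interim data would make the loss larger; correlation with OS or very large true effects would make it smaller. Hochberg steps lower the levels in every scenario and keep the ordering. The point applies only if the formal interim OS analysis is run and met, about 36% likely at the design effect; the 60% figure belongs to a branch of about 6% or less.

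**What to change.** In SAP 8.2.2, scenarios A and C and footnote 2, state that key secondary endpoints not rejected at the interim are re-tested by Hochberg at the final OS analysis at 1-sided 0.020 (2-sided 0.040), if the trial continues to 508 deaths. Correct footnote 2 at the same time: it is conditioned on final OS being met, but it is attached to A and C, where final OS is not tested. It should refer to interim OS.

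The cost is one more confirmatory look, which must be described. No extra data are needed, because the footnote already produces these final results descriptively. SAP wording alone is not enough: Protocol 8.2 requires an amendment when methods for key secondary hypotheses change. Both changes must be fixed before unblinded results are seen; after that, the final secondary results should stay descriptive.
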